12.8.3. Interpretation of Definitions

AE Reporting Period

The study period during which AEs must be reported is normally defined as the time of consent to the end of the study treatment follow-up. However, for this study, the AE reporting period will be divided based on the three phases of the study.

a. **Screening phase:** When all screening tests have been done, we will assess for any AEs related to the screening tests at the time of communication with the subject about whether he/she is officially eligible or ineligible for the study.

Preexisting Condition: A preexisting condition is one that is present at the start of the study. A preexisting condition should be recorded as an AE if the frequency, intensity, or the character of the condition worsens during the study period.

b. **Waitlist phase:** We will only capture AEs that are pertinent to the study. Specifically the following will be captured:

1. Patient death,
2. Patient develops a condition that would exclude them from the study,
3. Patient is de-listed (taken off the lung transplant waitlist),
4. Patient is made inactive on the transplant waitlist,
5. Patient is transplanted with a non-HCV lung.

In order to ascertain these events, we will review the patient's medical record once a month, and will contact the patient (by phone, e-mail, or in-person) every 6-8 weeks.

c. **Post-transplant phase:** All AEs will be assessed at every clinic visit when the subject is seen by a member of the study team.

d. **Post-study:** At the last scheduled visit, the investigator will instruct each subject to report any subsequent event(s) that the subject, or the subject's personal physician, believes might reasonably be related to participation in this study.

All unresolved AEs considered possibly, probably or definitely related to the study drug should be followed by the investigator until the events are resolved, the subject is lost to follow-up, or the AE is otherwise explained. The investigator should notify the IRB of any death or AE occurring at any time after a subject has discontinued or terminated study participation that may reasonably be related to this study. The IRB will also be notified if the investigator should become aware of the development of cancer or of a congenital anomaly in a subsequently conceived offspring of a subject that has participated in this study.

General Physical Examination Findings (screening, post-transplant, and post-study phases)

At screening, any clinically significant abnormality should be recorded as a preexisting condition. At the end of the study, any new clinically significant findings/abnormalities that meet the definition of an AE must also be recorded and documented as an AE.

Abnormal Laboratory Values (post-transplant, and post-study phases)

A clinical laboratory abnormality should be documented as an AE if any one of the following conditions is met:

- The laboratory abnormality is considered clinically significant by the local PI and is not otherwise refuted by a repeat test to confirm the abnormality
- The abnormality suggests a disease and/or organ toxicity
- The abnormality is of a degree that requires active management; e.g. change of dose, discontinuation of the drug, more frequent follow-up assessments, further diagnostic investigation, etc.

Hospitalization, Prolonged Hospitalization or Surgery (post-transplant and post-study phase)

Any AE that results in hospitalization or prolonged hospitalization should be documented and reported as a serious AE unless specifically instructed otherwise in this protocol, with the exception of hospitalization at the time of a lung offer and/or lung transplant. Any condition responsible for surgery should be documented as an AE if the condition meets the criteria for an AE.

Neither the condition, hospitalization, prolonged hospitalization, nor surgery are reported as an AE in the following circumstances:

- Hospitalization or prolonged hospitalization for diagnostic or elective surgical procedures for a preexisting condition. Surgery should **not** be reported as an outcome of an AE if the purpose of the surgery was elective or diagnostic and the outcome was uneventful.
- Hospitalization or prolonged hospitalization for therapy of the target disease of the study, unless it is a worsening or increase in frequency of hospital admissions as judged by the clinical investigator.

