7.1.2. Administration of Zepatier

Merck & Co will manufacture, package, and label Zepatier drug. There will be one bottle per subject containing a 28-day supply (28 capsules) of 100/50 mg Zepatier tablets. Daily dose will be one tablet.

The Investigational Drug Services (IDS) pharmacy, directed by [name], will only be required to store and distribute Zepatier. Sofosbuvir and Ribavirin will be purchased and sourced locally. Both of these medications will be purchased and stored by the IDS pharmacy at Penn. Ribavirin will be generic and the manufacturer will vary depending on monthly price fluctuations.

Zepatier will be picked up from the investigational drug services (IDS) pharmacy by the research staff at 28-day intervals. The study staff will deliver the medication to the subjects at their study visits (patients expected to be at home by the time that HCV therapy is initiated and patients will be given medication at their scheduled post-transplant/study visit). Treatment with the study drug will begin within 4 weeks post-transplant. If hepatitis C is not cured after a subject has received Zepatier, he or she will be treated with a second regimen that includes Zepatier plus Sovaldi (Sofosbuvir) and Ribavirin. Any patient (male or female) receiving ribavirin as part of the first- or second-line regimen will be required to use two methods of birth control while on Ribavirin therapy, with continuing two forms of birth control for up to 6 months after the last dose of the study drug.

If patients have baseline NS5A drug resistance assay testing that demonstrates polymorphisms at positions M28, Q30, L31, and/or Y93, treatment with Zepatier will be extended to 16 weeks, rather than 12 weeks, and renally-adjusted Ribavirin at the clinician's discretion will be initiated, and continued for the remainder of therapy (until the 16 week mark). Such a strategy will provide optimal treatment, without delaying therapy prior to receipt of results of NS5A drug resistant testing.

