8.1.3.3. Visit 1: Post-Lung Transplant (between days 2 - 7)

The study staff will meet the subject in their HUP hospital room, three days after their lung transplant.

Initiating antiviral treatment

Treatment with the study drug will begin when the patient has a detectable and quantifiable HCV RNA post-transplantation and the donor and/or recipient have had an HCV genotype ascertained to guide treatment. As appropriate, subjects being discharged will be provided with a sufficient supply of the study drug.

As with any scientific protocol, safety will be considered before treating the patients. The treating physician will evaluate the patient's overall condition and make a judgment on whether initiating treatment is safe.

The following research procedures and activities will be performed:

- Assess for Adverse Events
- Obtain medication data
- Research Phlebotomy, including the NS5A drug resistance assay testing as appropriate (See Section 8.2.1 for complete list)
- Dispense study drugs

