8.2. Study schedule of procedures

8.2.1. Visits, lab testing, and other clinical testing

See next page for table.

Transplanting HCV Lungs into HCV Negative Lung Recipients

Protocol V5.0, November 2020

Week(s) post-KT		Day(s) post-KT		Visit Schedule		Research Visit Activities					Research Labs					Standard of Care								
Week(s) post-KT	Day(s) post-KT	Visit	Study Visits	Lab-Only	Informed Consent	Assess Adverse Events	Current Medications	Fibroscan	RAND-36 Questionnaire	HBV DNA HIV AB & LFTs	HBV Core Antibody	Urine Preg Test	Urine Protein/Cre Ratio	HCV RNA	Viral Kinetics (optional)♦	NSSA Resistance**	Genotyping of donor and/or recipient	Vitals & Physical Exam	Surveillance biopsy	CMP*	CBC	Tacrolimus		
Screening					✓	✓	✓	✓	✓	✓	✓	✓	✓	✓				✓						
1 (Begin treatment)	Day 2 - 7	V1	✓			✓	✓				✓■			✓	✓	✓	✓	✓	✓	✓	✓	✓		
1	7 ± 1 day			✓			✓							✓	✓					✓	✓	✓	✓	
2	10 ± 1 day	V2	✓			✓	✓							✓	✓				✓	✓	✓	✓	✓	
2	14 ± 1 day			✓			✓							✓	✓				¥	✓	✓	✓	✓	
3	21 ± 3 day	V3	✓			✓	✓							✓	✓				✓	✓	✓	✓	✓	
4	28 ± 3 day	V4	✓			✓	✓	✓	✓					✓	✓	✓			✓	✓	✓	✓	✓	
6	42 ± 7 day	V5	✓			✓	✓				✓■			✓	✓				✓	✓	✓	✓	✓	
8	56 ± 7 day	V6	✓			✓	✓							✓	✓				✓	✓	✓	✓	✓	
10	70 ± 7 day	V7	✓			✓	✓								✓				✓	✓	✓	✓	✓	
12	84 ± 7 day	V8	✓			✓	✓				✓■			✓	✓	✓			✓	✓	✓	✓	✓	
13 (End treatment)†	91 ± 7 day			✓			✓								✓									
16 (SVR 4)†	112 ± 14 day	V9	✓†			✓	✓							✓	✓			✓†	✓	✓	✓	✓	✓	
20 (SVR 8)	140 ± 7 day			✓										✓	✓				✓	✓	✓	✓	✓	
24 (SVR 12)	168 ± 14 day	V10	✓			✓		✓	✓					✓	✓	✓			✓	✓	✓	✓	✓	
28†	196 ± 7 day			✓											✓					✓	✓	✓	✓	✓
32	224 ± 7 day			✓											✓					✓	✓	✓	✓	✓
36 (SVR 24)	252 ± 7 day			✓										✓	✓	✓			✓	✓	✓	✓	✓	
40	280 ± 14 day			✓										✓					✓	✓	✓	✓	✓	
52	365 ± 14 day	V11	✓			✓		✓	✓					✓	✓	✓			✓	✓	✓	✓	✓	

* CMP=comprehensive metabolic panel which includes basic metabolic panel and liver function tests
care blood draw

** As appropriate ♦Viral Kinetics testing can be done anytime there is a standard of

[†]If patients require the 16 weeks of therapy, the last 4 weeks would be the same as weeks 9-12 of therapy [■]Only if HBV Core Antibodies are positive.

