12.8. Safety and Adverse Events

12.8.1. Definitions

Adverse event (AE): Any untoward medical occurrence associated with the protocol procedures, whether or not considered product or process related. Any symptom, sign, illness or experience that develops or worsens in severity during the course of the study. Inter-current illnesses or injuries should be regarded as AEs. Abnormal results of diagnostic procedures are considered to be AEs if the abnormality:

- results in study withdrawal
- is associated with a serious AE
- is associated with clinical signs or symptoms
- leads to additional treatment or to further diagnostic tests
- is considered by the investigator to be of clinical significance

Serious adverse event (SAE): Adverse events are classified as serious or non-serious. A *serious adverse event* is any AE that is:

- fatal
- life-threatening
- requires or prolongs hospital stay
- results in persistent or significant disability or incapacity
- a congenital anomaly or birth defect
- an important medical event

Important medical events are those that may not be immediately life threatening, but are clearly of major clinical significance. They may jeopardize the subject, and may require intervention to prevent one of the other serious outcomes noted above. For example, drug overdose or abuse, a seizure that did not result in in-subject hospitalization or intensive treatment of bronchospasm in an emergency department would typically be considered serious.

All AEs that do not meet any of the criteria for serious should be regarded as *non-serious AEs*.

Suspected adverse reaction: Any adverse event for which there is a reasonable possibility that the drug/investigational product caused the adverse event. For reporting purposes, "reasonable possibility" means there is evidence to suggest a causal relationship between the drug/investigational product and the adverse event.

Unanticipated Adverse Device Effect (ADE): is any serious adverse effect on health or safety, or any life-threatening problem or death caused by, or associated with, a device, if that effect, problem, or death was not previously identified in nature, severity, or degree of incidence in the investigational plan or application, or any

other unanticipated serious problem associated with a device that relates to the rights, safety, or welfare of subjects.

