12.11. Potential Risks

12.11.1. Risks of Study Procedures

There are several areas of potential risk in this study. We will obtain several blood samples from each subject. There is a risk of bruising, hematoma, and infection after phlebotomy, which are possible but not considered serious AEs. Fainting may occur, which is unlikely but considered a serious AE. The removal of <70 cc of blood every 1-4 weeks during the 40-week post-transplant period is a potential risk; however this amount is routinely taken from subjects for clinical indications without adverse effect. Study medications will be delayed until after phlebotomy on each study day.

Because we may store subjects' blood samples, there may be confidentiality risks associated with the storage and analysis of those samples or the information resulting from the analysis of those samples. Samples may be used for genetic testing. Under some circumstances, it can be a risk for genetic information to be known. To help ensure confidentiality, samples will be coded and stored in a secured facility. While situations cannot be foreseen where potentially sensitive genetic information is revealed or where people who should not have this information could obtain it (representing a loss of confidentiality), however, it is possible that presently unforeseen situations may arise where this could happen.

The risk of undergoing screening includes potential identification of new health problems that subjects were unaware of. If we discover new health problems, we will answer subjects' questions and try to arrange appropriate treatment if any is needed. If new health problems are discovered, it is possible that subjects would not be able to enter this study. It is also possible that subjects would no longer be eligible for lung transplantation based on the results.

The risks of lung transplant surgery include blood loss, infections, and deep vein thrombosis. There are also risks related to immunosuppression and standard anti-infective therapy.

The risks of any transplant include primary graft non-function, delayed graft function, acute rejection, and death. Re-admissions within 30 days after a lung transplant are expected in approximately 40% of patients.

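### Two passages depart from the SAE definition in 12.8.1: every phlebotomy faint is classed as serious, and the transplant-admission exception is ambiguous about AEs that prolong the stay

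*Combined protocol and SAP*

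**What the plan says.** **Definition.** Section 12.8.1 makes an AE serious if it "requires or prolongs hospital stay". The other criteria are death, threat to life, lasting disability, congenital anomaly and important medical event. No admission is carved out.

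**Hospitalization rule.** Section 12.8.3 restates the hospital criterion: "Any AE that results in hospitalization or prolonged hospitalization should be documented and reported as a serious AE unless specifically instructed otherwise in this protocol". It then adds "with the exception of hospitalization at the time of a lung offer and/or lung transplant".

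**Phlebotomy.** Section 12.11.1 labels bruising, hematoma and infection after a blood draw as not serious, and continues: "Fainting may occur, which is unlikely but considered a serious AE".

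**Start of dosing.** Section 8.1.3.3 (Visit 1, days 2 to 7) says "The study staff will meet the subject in their HUP hospital room, three days after their lung transplant" and lists dispensing of study drug among the activities, subject to a quantifiable HCV RNA and a known genotype. The schedule in 8.2.1 marks the day 2 to 7 row as the start of treatment. Section 7.1.2 instead describes "patients expected to be at home by the time that HCV therapy is initiated", with a start within 4 weeks of transplant.

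**Use of SAEs.** Section 5.2 makes safety of treatment a primary objective. Under 12.8.4, an unexpected, related event that prolongs hospitalization goes to the IRB within 3 calendar days. Under 12.8.4.1, every SAE goes to the drug supplier within 2 working days, and no later than 3 calendar days. Under 10.6, the DSMB evaluates SAEs.

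**The concern.** An SAE count can be interpreted only if the same event is classified the same way by everyone who applies the protocol. Here two passages outside the definition can change the classification.

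The faint rule attaches the serious label to a symptom and asks for no outcome. Followed literally, it puts non-serious events into the SAE count and into expedited forwarding.

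The exception in 12.8.3 can be read in two ways, and one of them takes away the prolongation criterion during the transplant admission. An AE whose only serious feature is a longer first stay could then miss the IRB, drug supplier and DSMB routes. That stay is when events related to the HCV-positive lung are plausible, and 9.2.1 counts those as part of safety. If dosing starts at days 2 to 7, some early drug exposure falls there too.

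**Working it through.** The plan gives no SAE rate, target or stopping threshold, so there is no figure to reproduce. The main check is textual. The arithmetic only shows scale.

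**1. Faint rule against the definition.** A brief faint with full recovery is not fatal, life-threatening or disabling, and need not require or prolong a hospital stay. It could count as an important medical event, but 12.8.1 reserves that for events of major clinical significance, case by case. Section 12.11.1 settles the matter in advance for every faint. It also does so in the other direction for infection after a draw. Because the 12.8.3 rule gives way where the protocol instructs otherwise, that fixed label could be taken to override it.

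**2. Exception against the definition.**
- Narrow reading: only the planned admission is excepted. An AE that prolongs it is still an SAE, so 12.8.1, 12.8.3 and the reporting table in 12.8.4 agree. Nothing is lost.
- Broad reading: AEs linked to that stay, including those that prolong it, are excepted. This contradicts 12.8.1 and the 12.8.4 row that names prolonged hospitalization.

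Nothing in 12.8 says which reading applies.

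**3. Weight of one subject.** N = 11 (synopsis; 6.1). 1/11 = 9.1 percentage points, if the subject has no other SAE. Exact 95% intervals: 4/11 (36%) gives 11% to 69%; 5/11 (45%) gives 17% to 77%.

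**4. Faint rule, scale.** Inputs: 17 draws per subject (rows of the 8.2.2 table) or 19 (post-transplant rows of 8.2.1). The faint risk per draw, f, is assumed to be 0.05% to 1%. As a stand-in for subjects who already have an SAE, I use the 40% readmission expected within 30 days (12.11.1).
- Draws: 11 × 17 = 187, or 11 × 19 = 209.
- Expected faints in 187 draws: 187 × 0.0005 = 0.09 to 187 × 0.01 = 1.9. In 209 draws: 0.10 to 2.1.
- Added to the any-SAE proportion: 0.6 × [1 − (1 − f)^d], where d is draws per subject. For d = 17, f = 0.05%: 0.6 × 0.0085 = 0.5 points (0.06 of 11 subjects). For d = 19, f = 1%: 0.6 × 0.1738 = 10.4 points (1.1 of 11 subjects).

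**5. Exception, scale.** Assume that a share q of 10% to 30% of subjects have an AE whose only serious feature is prolonging the transplant stay, independent of the 40%.
- Narrow reading: 0 subjects missed.
- Broad reading: the any-SAE proportion reads 40% instead of 1 − 0.6 × (1 − q), which is 46% to 58%. Subjects missed: 11 × 0.6 × q = 0.7 to 2.0.

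**6. Overlap with dosing.** Take a first dose on day 3 (8.1.3.3). Section 8.1.3.4 has the subject come to the outpatient clinic at day 10. Planned overlap is at most (10 − 3)/84 = 8% of a 12-week course at the nominal days. Under 7.1.2 it is 0%.

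**The case against.** The best defence is that 12.8.3 treats hospitalization and prolonged hospitalization as separate terms, and the exception names only the first. Mentioning a lung offer alongside the transplant also fits a clause meant to stop a planned admission from counting as an SAE. This is a fair reading, and on it nothing is lost. It is not decisive. The rule concerns AEs that result in hospitalization, and a planned transplant admission does not result from an AE, so on the narrow reading the exception removes almost nothing. Ambiguous is the right word.

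Second, even the broad reading lifts only one criterion. Fatal, life-threatening, disabling and important medical events remain SAEs. The safety analysis (10.3, 10.6) tabulates incidence and grade of toxicities, and Grade 3 in 12.8.2 includes prolongation of hospitalization, so such an event would still appear as severe. This stands and limits the harm mainly to SAE counts and expedited reporting.

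Third, the faint sentence sits in a risk section and errs toward over-reporting. That makes it conservative, but it still disagrees with 12.8.1.

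A reader might infer that a substantial part of treatment, say 13% to 30%, falls under the exception. That needs an assumed 14 to 28 day admission: (14 − 3)/84 and (28 − 3)/84. The documents give no length of stay, place outpatient visits at days 10, 21 and 28, and conflict on whether dosing begins in hospital at all. Treatment days are also not misclassified events.

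**Conclusion.** SAE classification is internally inconsistent in two places.

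- **Faint rule: wrong as written.** It can only add SAEs. The addition is about 0.06 to 1.1 of 11 subjects, on an assumed 0.05% to 1% faint risk per draw, with 40% of subjects already having an SAE.
- **Exception: ambiguous.** The loss is zero on the narrow reading. On the broad reading it is about 0.7 to 2.0 of 11 subjects, if 10% to 30% have a prolongation-only event. That share is an assumption. No other kind of serious event is affected.

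One might conclude that the trial's SAE rate is wrong in both directions. The documents do not support that: no rate or threshold is stated, the undercount depends on the reading, and the faint effect is small unless the risk per draw is near 1%. What can be said is that the faint rule misclassifies simple faints, and that the exception allows two study staff to classify the same event differently. With 11 subjects, either can move the reported proportion by 9.1 points per subject.

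Sections 7.1.2, 8.1.3.3 and 8.2.1 also disagree on where and when dosing starts. The planned overlap with the transplant stay is therefore about 0% to 8% of an 84-day course.

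**What to change.** 1. In 12.8.3, state that only the planned admission for the lung offer or transplant is excepted, and add: *An AE arising after transplant that prolongs this admission is an SAE.* If the narrow reading was intended, this only says so.
2. In 12.11.1, replace the fixed serious and non-serious labels for phlebotomy events with: *classified under 12.8.1*.
3. Reconcile 7.1.2 with 8.1.3.3 and 8.2.1 on where and when treatment starts, so that it is clear which part of exposure falls within the transplant admission.

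The first two changes are one sentence each and affect event classification only. The cost is a few more SAE forms from the first admission.

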12.8.4. Reporting Procedures for Unanticipated Problems, Adverse Events, and Adverse Device Effects

Principal investigators should notify and local IRB, in an expedited manner, of those events related to study participation that are unforeseen and indicate that participants or others are at increased risk of harm.

Researchers should submit reports of the following problems:

Any AE/ADE or UP (regardless of whether the event is serious or non-serious, on-site or off-site) that occurs any time during or after the research study, which in the opinion of the principal investigator is:

Unexpected (An event is “unexpected” when its specificity and severity are not accurately reflected in the protocol-related documents, such as the IRB-approved research protocol, any applicable investigator brochure, and the current IRB-approved informed consent document and other relevant sources of information, such as product labeling and package inserts.)

AND

Related to the research procedures (An event is “related to the research procedures” if in the opinion of the principal investigator, the event was more likely than not to be caused by the research procedures.)

AND

Suggests that the research places subjects or others at a greater risk of harm (including physical, psychological, economic, or social harm) than was previously known or recognized.

Additionally, all adverse events/adverse device effects shall be documented by the PI team, assessed, and shared with. All Serious Adverse Events will be forwarded to **Merck Worldwide Product Safety**.

What Event is Reported	By Whom is Event Reported	To Whom is Event Reported	When is Event Reported
Fatal unexpected, suspected serious adverse event (SAE/ADE – death that is unexpected and poss/prob/def related to the research)	Investigator	Local IRB	Within 24 hours of initial receipt of information

Life-threatening unexpected, suspected serious adverse reactions (SAE/ADE- life-threatening, unexpected, poss/prob/def related to the research)	Investigator	Local IRB	
Non-fatal, non-life-threatening unexpected, suspected serious adverse reactions (SAE/ADE – unexpected, poss/prob/def related, non-life-threatening hospitalization, prolonged hospitalization, disability/incapacity/birth defects, important medical event)	Investigator	Local IRB	Within 3 calendar days of initial receipt of information
Unanticipated Problem that is not an SAE (AE/ADE or non-AE, unexpected, poss/prob/def related and suggests greater risk of harm) e.g. Development of moderate hypersomnia that resolve after discontinuing drug. This AE/ADE although not-serious, is not listed as an expected event in the consent. Thus it is an AE that is unexpected, possibly related (resolved after coming off drug), and places subject(s) at greater risk of harm than previously known	Investigator	Local IRB	Within 10 calendar days of initial receipt of information

